### 8.2.3 48-hour Urine Volume

Urine volume will be recorded by the patient in his or her patient diary during the defined 48-hour measurement periods prior to a trial visit and transcribed to the eCRF. During this time the patient must adhere to the individually predefined drinking menu (up to Visit 9, see Section 8.2.2). The patient will be provided with urine measuring cups.

The 48-hour urine volume measurements should occur as close as possible to and within 7 days of the coming site visit. For patients with SBS-IF the measurements should be timed with the PS schedule. Patients on PS 7 days weekly must perform the 48-hour measurement on 2 consecutive

days on PS. Patients on PS 1-6 days weekly must record the 48-hour measurement at 1 day on PS and 1 day off starting on the day on PS.

See Table 8 for further clarity. The grey boxes indicate the possible 48-hour urine measurement periods. If more than 1 interval is available anyone of them can be chosen.

The patient should perform the 48-hour measurement on the same days of the week during each period as long as the PS regimen remains the same. The selected days will be recorded in the patient diary. If the PS regimen changes during the trial, a new schedule for 48-hour measurement can be chosen.

PS days/ Week 48-hour measurement Day 1 Day 2 Day 3 Day 4 Day 5 Day 6 Day 7 7 days 2 days on PS 3 6 days 1 day on PS + 1 day off PS 1 5 days 1 day on PS + 1 day off PS 1 2 3 5 4 days 1 day on PS + 1 day off PS2 3 3 days 1 day on PS + 1 day off PS2 2 days 1 day on PS + 1 day off PS2 1 day 1 day on PS + 1 day off PS0 days 2 days off PS

Table 8 Timing of 48-hour periods and balance studies

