2.2.1 Metabolic Balance Study

An 48-hour MBS will be conducted at baseline (V1) and at V9. The start of the 48-hour sample collection should be on Day 2 of the MBS in the morning, collection continues throughout Day 3 of the MBS and ends on Day 4 of the MBS in the morning.

Several efficacy parameters of the MBS are collected separately for the first and second 24-hour period:

- oral wet weight intake [solid and fluid]
- wet weight output [fecal and urinary]
- energy intake and output
- intake and fecal output of macronutrients
- intake and fecal output of electrolytes and
- urinary excretion of electrolytes.

Data for the first 24-hour period are documented in the eCRF at Day 2 (MBS) and data for the second 24-hour period are documented in the eCRF at Day 3 (MBS). To obtain per day measures for these parameters, values of the first and second 24-hour period will be averaged.

Thus, the following formula is used to obtain an average per day measure at baseline:

Efficacy data item (unit/d) =

{Efficacy data item (unit/d) [Visit 1 – Week 0 – Day 2 (MBS)] + Efficacy data item (unit/d) [Visit 1 – Week 0 – Day 3 (MBS)]} / 2

In case one of the measures assessed for the first or second 24-hour period (Day 2 or Day 3 in the eCRF) is missing, the per day measure is obtained as follows:

For patients without parenteral support (PS):

If at least one of the two 24-hour measurements from the assessments of the 48-hour MBS period is recorded, the assessment will be used in the analysis.

For patients with PS:

As data recorded during one of the 24-hour period (on PS) is not representative for the other 24-hour period (off PS), both assessments need to be available to use the average of these values for analysis.

In case both 24-hour measuresments are missing, the respective average per day measure is also missing.

Analogously, the efficacy data items for Week 24 are calculated based on the information in the eCRF at Visit 9 – Week 24 – Day 2 (MBS) and Visit 9 – Week 24 – Day 3 (MBS).

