• Absorption of electrolytes (sodium, potassium, calcium and magnesium): Change from baseline to Week 24 measured by 48-hour metabolic balance studies.

Absorption of electrolytes during the MBS at V1 and V9 is measured as oral intake (liquid and solid) minus fecal output.

Then Absorption of Electrolytes: Sodium (mmol/d) is calculated as

Absorption of Electrolytes: Sodium (mmol/d) =

Electrolytes: Sodium intake (mmol/d) - Electrolytes: Sodium fecal output (mmol/d)

The calculation of the following items

- Electrolytes: Sodium intake (mmol/d)
- Electrolytes: Sodium fecal output (mmol/d)

is done as described in Section 2.2.3.

Absorption of Electrolytes: Sodium (mmol/d) will be analyzed at Baseline and Week 24. Change from baseline to Week 24 for Absorption of Electrolytes: Sodium (mmol/d) is calculated as described in Section 2.1.2 and will be analyzed at Week 24.

Furthermore,

- Absorption of electrolytes: Potassium (mmol/d),
- Absorption of electrolytes: Calcium (mmol/d) and
- Absorption of electrolytes: Magnesium (mmol/d)

as well as their changes from baseline to Week 24 are calculated and analyzed analogously to Absorption of Electrolytes: Sodium (mmol/d) and its change from baseline to Week 24.

- For patients with Short Bowel Syndrome with Intestinal Failure (SBS-IF) only:
 - Weekly parenteral support (PS) volume: Change from baseline to Week 12 and 24.

PS volumes (mL) are documented by the patient in the diary and then transcribed to the eCRF page "Diary PS use". Weekly PS volume (mL) at a certain visit is calculated as sum of PS volumes (mL) for all PS bag ids over the seven days of the preceding week (date of visit -1 to date of visit -7) based on the information in the eCRF.

Here the date of visit used at baseline is the date of Visit 1 – Week 0 – Day 4 as documented in the eCRF. At Week 24, the date of Visit 9 – Week 24 – Day 4 is used. Weekly PS volume (mL) will be missing, in case any unknown volume is documented.

In case information on Diary PS use in the week before the baseline visit is available for less than seven days, weekly PS volume (mL) at baseline is determined based on prescribed PS over the seven days before the date of Visit 1 – Week 0 – Day 4. Thus, all PS prescriptions which are valid on date of "Visit 1 – Week 0 – Day 3" are determined. Then, the Weekly PS volume (mL) at baseline is calculated as sum of all weekly volumes (L) for these prescriptions as documented in the eCRF and multiplied by 1000.

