- Urinary excretion of electrolytes: Calcium (mmol/d) [based on eCRF information "Urinary electrolytes: Calcium (mmol/d)"],
- Urinary excretion of electrolytes: Magnesium (mmol/d) [based on eCRF information "Urinary electrolytes: Magnesium (mmol/d)"], and
- Urinary excretion of electrolytes: Urea (mmol/d) [based on eCRF information "Urinary electrolytes: Urea (mmol/d)"]

as well as their changes from baseline to Week 24 are calculated and analyzed analogously to Urinary excretion of electrolytes: Sodium (mmol/d) and its change from baseline to Week 24.

• Fluid Composite Effect: Change from baseline to Week 12, 24 and 52.

The fluid composite effect has been defined as parenteral volume + oral fluid volume – urine volume. Thus, fluid composite effect (L/d) at a certain visit will be calculated as:

Fluid composite effect (L/d) = [current PS volume (L/week)/7] + [oral fluid volume (L/d)] - [urine volume (L/d)].

Oral fluid volume (L/d) is based on 48-hour total drinking volume during the 48-hour urine collection period in the week prior to a visit (V2 to V8 and V10 to V12) or on the 48-hour total drinking volume during the MBS at V1 and V9:

Oral fluid volume (L/d) = [48-hour total drinking volume (mL)/1000]/2

Urine volume (L/d) is based on the total urine volume during the 48-hour urine collection period in the week prior to a visit (V2 to V8 and V10 to V12) or on the 48-hour urine volume collected during the MBS at V1 and V9.:

Urine volume (L/d) = [48-hour total urine volume (mL)/1000]/2

Current PS volume (L/week) will be derived as described in Section 2.3.2.

Fluid composite effect (L/d) will be analyzed at Baseline, Week 12, Week 24 and Week 52 (EOT). Changes from baseline to Week 12, Week 24 and Week 52 (EOT) are calculated as described in Section 2.1.2 and will be analyzed at Week 12, Week 24 and Week 52 (EOT).

• Drinking volume during 48-hour periods: Change from Week 24 to 52.

Drinking volume during 48-hour periods is based on the eCRF item Drinking volume: 48-hour total drinking volume (mL) and will be analyzed at Baseline, Week 24 and Week 52 (EOT). Change from Week 24 to Week 52 (EOT) for Drinking volume during 48-hour periods is calculated as described in Section 2.1.2 and will be analyzed at Week 52 (EOT).

- For patients with SBS-IF only:
 - Weekly PS volume: Change from baseline to Week 52.

Calculation of current weekly PS volume has been described in Section 2.3.2.

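### The fluid composite effect sets a 7-day PS mean against urine from a 48-hour window with a fixed on/off split, so a change in PS days per week can move it with no change in absorption

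*SAP*

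**What the plan says.** Protocol 8.2.21 defines the composite as parenteral plus oral fluid volume minus urine volume and sets no time base. SAP 2.4 supplies one: "Fluid composite effect (L/d) = [current PS volume (L/week)/7] + [oral fluid volume (L/d"), less urine, with "Urine volume (L/d) = [48-hour total urine volume (mL)/1000]/2". Oral volume is halved from a 48-hour total in the same way. Under SAP 2.3.2 the weekly PS volume "is calculated as sum of PS volumes (mL) for all PS bag ids over the seven days of the preceding week".

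The 48-hour window comes from protocol 8.2.3. Patients on PS 1-6 days a week "must record the 48-hour measurement at 1 day on PS and 1 day off starting on the day on PS". Those on PS every day record two days on PS, and Table 8 gives two days off for those on none. For the balance studies at Visits 1 and 9, protocol 8.2.1 asks only for a preference: one PS day followed by one day without. The title of Table 8, "Timing of 48-hour periods and balance studies", brings those visits under the same scheme, including two on-days at 7 days a week.

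The documents expect regimens to change. Weekly days on PS is an endpoint of its own, and protocol 8.2.3 states: "If the PS regimen changes during the trial, a new schedule for 48-hour measurement can be chosen".

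SAP 2.2.1, on missing balance-study data, also says: "As data recorded during one of the 24-hour period (on PS) is not representative for the other 24-hour period (off PS"). SAP 4.3.4 makes all exploratory endpoints descriptive, on the FAS.

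**The concern.** The PS term averages over a week and the urine term over two days, and the share of on-PS days in those two days does not follow the week. A patient on PS 6 days a week and one on 2 days both contribute half on-PS urine, while their PS terms reflect 6/7 and 2/7. If urine is higher on PS days, the 48-hour mean understates weekly urine for the first patient and overstates it for the second.

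The error does not cancel in a change from baseline when PS days change, because it depends on the number of PS days. Fewer PS days is a response this trial looks for. A change in infusion schedule could then be read as a change in fluid balance.

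**Working it through.** The documents state no figure for the composite, so there is none to reproduce. Their PS adjustment example (protocol 8.2.9) does reproduce: 10 - 7 x 0.2 = 8.6 L/week.

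**Notation.** k = PS days a week. v = litres per PS day. s(k) = on-PS share of the window: 1/2 for k = 1-6, 1 at k = 7, 0 at k = 0 (protocol 8.2.3). f = share of an infusion by which on-PS urine exceeds off-PS urine. c = share of that extra urine passed on the following day. Neither f nor c is in the documents, so ranges are shown.

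**Error without carry-over (c = 0).** The PS-driven part of weekly mean urine is f·v·k/7. The window records f·v·s(k). The composite is therefore off by

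E(k) = f·v·(k/7 - s(k)),

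and the false shift is E(after) - E(before). E is zero at k = 7 and at k = 0, so a move from 7 to 0 days produces no shift.

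**Protocol example.** Assume that drinking and weekly mean urine are back at baseline after the cut. The true change is then -1.4/7 = -0.20 L/day. Take the cut as one PS day fewer, with v = weekly volume/k.

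- 7 to 6 days: (8.6/6) x (6/7 - 1/2) - 0 = +0.512 per unit of f
- 6 to 5 days: (8.6/5) x (5/7 - 1/2) - (10/6) x (6/7 - 1/2) = -0.227 per unit of f
- 4 to 3 days: (8.6/3) x (3/7 - 1/2) - (10/4) x (4/7 - 1/2) = -0.383 per unit of f

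Change returned by the SAP formula (L/day, true value -0.20, c = 0):

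| PS days | f = 0 | f = 0.25 | f = 0.5 | f = 1 |
|---|---|---|---|---|
| 7 to 6 | -0.20 | -0.07 | +0.06 | +0.31 |
| 6 to 5 | -0.20 | -0.26 | -0.31 | -0.43 |
| 4 to 3 | -0.20 | -0.30 | -0.39 | -0.58 |

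Only the first row is close to dropping one day at constant volume per day (10 x 6/7 = 8.57 L). The other two also assume that volume per PS day rises: from 10/6 = 1.67 to 8.6/5 = 1.72 L, and from 10/4 = 2.50 to 8.6/3 = 2.87 L.

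One 7-to-6 patient would move a mean of five SBS-IF patients by at most 0.512/5 = +0.10 L/day. (Five is half of the 10 patients in protocol 9.2.) If PS days do not change, the error in this example is f x (-0.2 + 0.7/k) at 3-6 days and zero at 7, so at most 0.08 L/day.

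**With carry-over.** At 6 PS days the day before an on/off window is always an on-day, so the window captures (1 + c)/2 of one infusion's extra urine per day. The 7-to-6 slope becomes (8.6/6) x (6/7 - (1 + c)/2) = 0.512 - 0.717c. The sign reverses when f x slope exceeds 0.20:

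- c = 0: above f = 0.20/0.512 = 0.39
- c = 0.2: above f = 0.20/0.369 = 0.54
- c = 0.5: slope 0.154, so even f = 1 gives -0.05
- limit: (0.512 - 0.20)/0.717 = 0.435; above this c no f reverses the sign

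**Does weighting urine by PS days help?** Replace 48-hour urine/2 by [k x on-day urine + (7 - k) x off-day urine]/7. I compared the absolute shift under the two formulas over all 62 combinations of two different PS-day counts and the status of the day before the window, at equal v.

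| c | weighted no worse than SAP |
|---|---|
| 0 | 62 of 62 |
| 0.2 | 57 of 62 |
| 0.5 | 51 of 62 |
| 0.75 | 22 of 62 |
| 1 | 29 of 62 |

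The worst exception at c = 0.5 (v = 2 L assumed, f = 1) is 6 to 5 days: +0.57 L/day weighted against +0.21 under the SAP formula.

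**The case against.** The strongest reply is that neither the size nor the direction is established. The SAP's remark that on-PS and off-PS days are not representative of each other belongs to a missing-data rule and gives no urine difference; at f = 0 there is no error. This stands, and it limits the point to what can happen.

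A reader might infer that the formula gives the wrong sign for a patient going from 7 to 6 PS days. The documents do not support that: it needs f above 0.39 with no carry-over, a higher f with some, and cannot occur above c of about 0.435. A reader might also infer that the weighted formula should replace the SAP's. That is not shown either, since weighting does worse in most combinations when carry-over is large.

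Three further replies have weight. The protocol example cuts volume and says nothing about days, so reading it as one day fewer is an assumption. The on/off split is only preferred at the balance studies, and Visit 1 enters every change from baseline. The protocol's own PS algorithm (8.2.9) also uses urine without weighting for PS days, so a weighted composite would stand on a different basis from the urine that drives PS changes.

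Finally, the stakes are small. The SAP plans patient listings of diary PS, drinking and urine volumes, the composite and weekly PS days, so an affected patient can be found. A listing shows that PS days changed, however, and not how much of the composite's movement is due to that.

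**Conclusion.** The mismatch of time bases is in the text and nothing in either document corrects it. In SBS-IF patients whose PS days change, the composite can shift with no change in absorption. In the protocol's example, taken as 7 to 6 days, a true -0.20 L/day is returned as anything from -0.20 to +0.31 L/day for f from 0 to 1 at c = 0, and the upper end falls as carry-over rises. These figures rest on assumed f and c, on drinking and weekly urine back at baseline, and on reading the cut as one PS day fewer. The documents do not say how often PS days will change.

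A reader might extend this to the trial's conclusions. It does not reach them: the endpoint is exploratory and descriptive, patients without PS are unaffected, and the primary and key secondary endpoints are computed from oral intake and fecal output, without the composite. It is an optional improvement.

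**What to change.** In SAP 2.4, for patients on PS 1-6 days a week, also derive the composite with

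urine (L/d) = [k x on-PS-day urine + (7 - k) x off-PS-day urine]/7.

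Use the two 24-hour urine volumes that SAP 2.2.2 already has transcribed to the eCRF, and take k as the number of days with any PS in the diary. First confirm from the infusion dates that the window held one on-day and one off-day. The SAP's baseline fallback averages days over prescriptions, which need not equal that count, so it should not supply k unchecked. At 0 or 7 days keep the current formula.

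Report the weighted version beside the current one. Where PS days changed, interpret a change in the composite only if the two agree. Agreement is a safeguard and not proof: in the c = 0.5 exception above, both versions err upward.

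Drinking needs no weighting while the fixed menu applies, up to Visit 9. After that, "Drinking volume during 48-hour periods is based on the eCRF item Drinking volume: 48-hour total drinking volume (mL"), so it could be weighted only if the diary holds a daily split. The general on/off wording in protocol 8.2.1 and SAP 2.2.1 should be reconciled with Table 8 for patients on PS 7 days a week.

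The cost is one added derivation and no new data. Both 24-hour volumes must be present. Leaning on a single day raises the SD of the urine term by sqrt{[(k² + (7 - k)²)/49]/0.5}: 1.23-fold at 1 or 6 days, 1.09 at 2 or 5, and 1.01 at 3 or 4, assuming independent days of equal variance.

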# **6.4** Treatment Compliance

# **6.4.1 Drug Treatment Compliance**

Throughout the trial, the Investigator will remind the patients to follow the trial procedures and requirements to encourage patient compliance.

During the trial, patients will mainly self-administer trial product at home. The first dose will be administered at the trial site.

Patients are requested to enter details regarding trial product administration (including date and time of the day as well as dispensing unit number) and injection site area used (i.e., abdomen, thigh) in the diary and transcribed to the eCRF.

Patients are to record PS use (including bag name, volume and infusion date) in the diary on an ongoing basis, and must be checked and transcribed into the eCRF at every visit by the Investigator.

When patients self-administer trial product at home, compliance with trial product administration will be assessed and documented in source documents at each visit where information is available. If any suspicion of non-compliance arises, the site must start a dialogue with the patient, re-emphasizing the importance of compliance, uncover barriers to compliance, and retrain the patient, if needed. This dialogue must be documented. Compliance will be assessed by cross-checking the following sources and comparing these to the expected use:

- Drug accountability information; visual inspection of returned autoinjectors
- Review of patient diaries

The Investigator must ensure that patients who temporarily discontinue treatment with trial product due to safety concerns, e.g. admission to hospital, are resuming treatment safely to avoid dehydration.

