# 8.2.4 Patient Diary

Patients will be required to complete diaries throughout the course of the trial. Patients will record the following:

- Details regarding trial product administration, including date and time of the day as well as injection site area used, i.e. abdomen or thigh
- PS use (SBS-IF only) including bag name, volume and infusion date on an ongoing basis
- Urine volume and oral fluid intake will be recorded by the patient during the defined 48-hour periods prior to a trial visit
  - The patient should perform the 48-hour measurement on the same days of the week during each period as long as the PS regimen remains the same. The selected days will be recorded in the patient diary.
- If the PS regimen changes during the trial, a new schedule for 48-hour measurement can be chosen and recorded in the patient diary

The Investigator (or designee) must review the patient's diary entries routinely throughout the entire trial period. If clarification of entries or discrepancies in the diary is needed, the patient must be questioned, and a conclusion made in the patient's medical record and in the diary. Care must be taken not to bias the patient.

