Additionally to the analysis time points stated in Section 2.3.2, weekly PS volume will be analyzed at Week 52 (EOT), and the change of weekly PS volume from baseline to Week 52 (EOT) will be analyzed at Week 52 (EOT).

• Weekly PS macronutrients (total and individual energy content of carbohydrates, lipids and proteins) and electrolytes (sodium, potassium and magnesium): Change from baseline to Week 52.

Calculation of weekly PS macronutrients and electrolytes has been described in Section 2.3.2.

Additionally to the analysis time points stated in Section 2.3.2, weekly PS macronutrients will be analyzed at Week 52 (EOT), and the change of weekly PS macronutrients from baseline to Week 52 (EOT) will be analyzed at Week 52 (EOT).

• Weekly days on PS: Change from baseline to Week 12, 24 and 52.

The number of weekly days on PS is derived based on the eCRF page "Diary PS use" as the sum of days in the week prior to the visit (date of visit -1 to date of visit -7) for which a volume has been documented (i.e. > 0 mL and not unknown) for at least one PS bag identifier. Here the date of visit used at baseline is the date of Visit 1 - Week 0 - Day 4 as documented in the eCRF. At Week 24, the date of Visit 9 - Week 24 - Day 4 is used. The number of weekly days on PS for a certain visit after baseline will be missing in case only unknown volumes have been documented for at least one day or if

the Diary PS use page is missing for at least one day in the time interval used for calculation.

In case information on Diary PS use in the week before the baseline visit is available for less than seven days, the number of weekly days on PS is derived based on prescribed PS over the week before the date of Visit 1 – Week 0 – Day 4. Thus, all PS prescriptions which are valid on date of "Visit 1 – Week 0 – Day 3" are determined. The number of weekly days on PS at baseline is then calculated as the average over the number of days per week as documented in the eCRF for all these prescriptions.

Weekly days on PS will be analyzed at Baseline, Week 12, Week 24 and Week 52 (EOT). Changes from baseline to Week 12, Week 24 and Week 52 (EOT) are calculated as described in Section 2.1.2 and will be analyzed at Week 12, Week 24 and Week 52 (EOT).

- For patients with SBS with intestinal insufficiency (SBS-II) only:
 - *Urine output: Change from baseline to Week 12, 24 and 52.*

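### SAP 2.4 discards a post-baseline weekly count of PS days when one day has only unknown volumes, although a documented bag normally shows that PS was given that day

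*SAP*

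**What the plan says.** SAP 2.4 (weekly days on PS, SBS-IF only) derives the count from the Diary PS use page over the seven days before the visit. A day counts if it is one "for which a volume has been documented (i.e. > 0 mL and not unknown) for at least one PS bag identifier".

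Two events set a post-baseline count to missing. The first is: "The number of weekly days on PS for a certain visit after baseline will be missing in case only unknown volumes have been documented". A single such day is enough. The second is that "the Diary PS use page is missing for at least one day in the time interval used for calculation".

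Baseline is treated differently. "In case information on Diary PS use in the week before the baseline visit is available for less than seven days", the SAP uses the prescribed number of days per week. It gives no such fallback after baseline.

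Protocol 6.4.1 says what the patient enters: "Patients are to record PS use (including bag name, volume and infusion date) in the diary on an ongoing basis". Protocol 8.2.4 lists the same items.

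For the related volume endpoint, SAP 2.3.2 says: "Weekly PS volume (mL) will be missing, in case any unknown volume is documented".

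**The concern.** A missing volume and a missing day count are different things. If a bag is entered against an infusion date and only the amount is unknown, the weekly volume cannot be summed, but whether PS was given that day is normally known. SAP 2.4 nevertheless drops the whole week's count, including the other six days.

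Under SAP 2.1.2.1 a missing visit value also makes the change from baseline missing. One unclear bag therefore takes the patient out of both the visit summary and the change summary at that time point. With about five SBS-IF patients, losing one is noticeable in a mean or median, and the information lost was in hand.

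**Working it through.** The documents give no sample size, power or rate for this endpoint, so there is no planned figure to reproduce. The check is of the derivation rule.

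**Inputs**
- Window: the seven days before the visit (SAP 2.4).
- Day definition: a known volume above 0 mL for at least one bag (SAP 2.4).
- Missing rule under review: at least one day with only unknown volumes, visits after baseline (SAP 2.4).
- Diary content: bag name, volume, infusion date (Protocol 6.4.1 and 8.2.4).
- Size of the subgroup: 10 patients to be enrolled with an equal SBS-II/SBS-IF split aimed for (Protocol 9.2), so 10/2 = 5. At the maximum of 16 enrolled (Protocol 4.1), 16/2 = 8.

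**Step 1. What an unknown volume tells us.** The diary entry is tied to a named bag and an infusion date. SAP 2.3.2, on PS bag contents, treats an unknown entry as an unknown amount of PS that was administered. On that reading the event is recorded and only its size is not.

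**Step 2. What the SAP already accepts.** A day with one bag of known positive volume and a second bag of unknown volume counts as a PS day. The day's total volume is unknown there too, so the day count does not depend on a complete volume.

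**Step 3. Example week.**

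| Days in the window | Number |
|---|---|
| Known volume above 0 mL | 4 |
| Only an unknown volume | 1 |
| 0 mL | 2 |

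- Present rule: one day has only unknown volumes, so the count is missing.
- Counting the documented bag as a PS day: 4 + 1 = 5.

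For weekly volume, missing is the right result for this week, because the sum cannot be formed. For days it is not needed.

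**Step 4. How often this could occur.** Assume an independent probability p, on each of the seven days, that only unknown volumes are documented. For a patient on PS every day, the chance of losing the week is 1 − (1 − p)^7. Patients with fewer PS days have fewer chances of an unknown volume, so these values are upper ends for each p.

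| Assumed p per day | Chance the week is missing | Expected lost of 5 | Expected lost of 8 |
|---|---|---|---|
| 1% | 6.8% | 0.34 | 0.54 |
| 2% | 13.2% | 0.66 | 1.05 |
| 5% | 30.2% | 1.51 | 2.41 |
| 10% | 52.2% | 2.61 | 4.17 |

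The p values are assumptions. The table shows how a seven-day all-or-nothing rule magnifies a small daily rate. It does not predict the loss in this trial.

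**The case against.** **An unknown volume is not proof of infusion.** Because 0 mL appears to be a recordable value, a bag entered with unknown volume could in principle be one that was not given. This stands as a caveat. Counting the day is the more natural reading of a dated bag entry, but it is a choice, so affected days should be visible.

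**Unknown volumes may be rare.** PS entries are checked and transcribed at every visit (Protocol 6.4.1), and unclear diary entries are queried with the patient (Protocol 8.2.4). This is a fair point, and the documents give no rate either way.

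**Nothing is hidden.** The endpoint is exploratory and no test is planned. The table format in SAP 7.1 shows the number missing, and diary PS use, prescriptions and weekly PS days are listed by patient (Listings 2-7.1, 2-9 and 2-26; the note to 2-26 names SBS-II although its title says SBS-IF). This limits the impact. It does not make the summary correct. A standard-error argument would add nothing, since SAP 7.1 reports the SD and quartiles.

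**Stronger readings that the documents do not support.**
- A reader might infer that the missing-page rule is equally wrong and that it removes fully weaned patients. A truly absent page leaves the day unknown: four known PS days, one absent page and two days at 0 mL bound the count at 4 to 5, and seven absent pages bound it at 0 to 7. Setting that week to missing agrees with SAP 4.5. The condition of a volume above 0 mL, and the baseline wording about fewer than seven days of information, suggest that PS-free days are entered. If they were not, every patient on PS 1 to 6 days a week would be missing at every post-baseline visit, which is not a plausible reading.
- A reader might also infer that the rule was simply copied from weekly volume. It was not. Volume is lost if any volume is unknown, whereas the day count is lost only if a day has nothing but unknown volumes.

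**Conclusion.** The point holds for the unknown-volume rule only. SAP 2.4 discards a post-baseline count that can normally be recovered from the diary: in the example week, 5 days become missing. This rests on one assumption, that a bag entered against an infusion date was at least partly given.

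The size is small: at each affected visit, one patient lost from about five in an exploratory, descriptive summary. How often this would happen cannot be stated from the documents. No confirmatory result is touched. The absent-page rule is defensible as written, and no loss of weaned patients is shown.

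**What to change.** In SAP 2.4, count a day as a PS day if at least one bag is documented as infused on that date, even if its volume is unknown, unless the volume is recorded as 0 mL. Delete the clause that sets the week to missing for a day with only unknown volumes. Keep the week missing when the Diary PS use page is truly absent for a day. The volume and content rules in SAP 2.3.2 need no change. Because the day definition also serves baseline, both ends of the change score would then use the same definition.

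Do not score 0 for every returned diary with no entry. That would turn incomplete diaries into PS-free days, which in an open-label single-arm trial favours the drug.

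The cost is a sentence of SAP wording and a small change in the derivation code before database lock. The downside is that a bag entered but not infused would count as a PS day. A flag in the patient listing, or a sensitivity summary under the present rule, covers this.
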